4. TREATMENTS

4.1 TREATMENTS TO BE ADMINISTERED

4.1.1 Identity of BI investigational product and comparator products

The investigational product dabigatran etexilate and the comparator warfarin will be supplied by Boehringer Ingelheim Pharma GmbH & Co. KG, Germany. The composition of these drugs capsules are detailed in Table 4.1.1: 1 and [Table 4.1.1:2](#).

Table 4.1.1: 1 Dabigatran etexilate (Investigational drug)

Substance:	Dabigatran etexilate
Brand name:	Pradaxa®
Pharmaceutical formulation:	Capsule
Source:	Boehringer Ingelheim Pharma GmbH & Co. KG, Germany
Unit strength:	110mg and 150mg
Total Daily dose	220mg; 300mg 1 x 110mg capsule b.i.d. (total daily dose 220mg) 1 x 150mg capsule b.i.d. (total daily dose 300mg)
Route of administration:	p.o.

The main excipients of the dabigatran capsule include tartaric acid, acacia, hypromellose, dimeticone, talc, hydroxypropylcellulose, HPMC (hydroxypropylmethylcellulose) capsule shell, consisting of titanium dioxide (E171), FD & C yellow 6/Sunset Yellow (E110), FD & C Blue 2/Indigo Carmine (E132), hypromellose carrageenan and potassium chloride.

Proprietary confidential information.

© 2016 Boehringer Ingelheim International GmbH or one or more of its affiliated companies. All rights reserved.

This document may not - in full or in part - be passed on, reproduced, published or otherwise used without prior written permission.

Table 4.1.1: 2 Warfarin (active comparator)

Substance:	Warfarin
Pharmaceutical formulation:	Tablet
Source:	Teva UK Limited, UK
Total Daily dose	1mg; 3mg; 5mg As needed to maintain a target INR of 2.0- 3.0 (2.0-2.5 if feasible)
Route of administration:	p.o.

For easy identification warfarin tablet strengths will have a different colour label.

The warfarin sodium tablets are composed of lactose monohydrate, starch (pregelatinised, maize), dispersed erythrosine lake, sodium starch glycolate and magnesium stearate.

Patients will take the warfarin q.d.. The individual doses will be titrated without splitting of the tablet as needed to maintain a target INR of 2.0 - 3.0. If feasible, an INR of between 2.0 – 2.5 should be targeted. INR will be measured at least every two weeks for the first three months in patients newly commencing warfarin, otherwise at least every month throughout the study (more frequently immediately after initiation of warfarin therapy or if required, according to clinical judgement).

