4.1.4 Drug assignment and administration of doses for each patient

Each patient will be randomised at Visit 2 to receive either dabigatran etexilate (110mg or 150mg b.i.d.) or warfarin. The first dose of trial medication will be taken, between 6 hours after sheath removal and preferably within 72 hours post PCI, with haemostasis assured, however up to 120 hours post PCI is allowed.

Patient randomised to receive dabigatran etexilate:

It is permitted for patients to receive bridging therapy with a parenteral anticoagulant according to local practice before switching to dabigatran etexilate. Dabigatran etexilate should be given 0-2 hours prior to the time that the next dose of parenteral anticoagulant would be due, or at the time of discontinuation in case of continuous treatment (e.g. intravenous (i.v.) unfractionated heparin (UFH)). See [Appendix 10.1](#) for guidance how to switch from an anticoagulant to dabigatran etexilate.

Dabigatran etexilate capsules should be taken in the morning and in the evening (one at each timepoint), at the same time every day with a full glass of water. The capsules must not be crushed, nor opened and can be taken with or without food. If dyspeptic symptoms occur, the Investigator should consider adding a proton pump-inhibitor (PPI) or H2-blocker to the concomitant therapy of the patients.

The interval between doses should be as close to 12 hours as possible.

If a dose of dabigatran etexilate is missed for any reason, the forgotten dose may still be taken up to six hours prior to the next scheduled dose. From six hours prior to the next scheduled

Proprietary confidential information.

© 2016 Boehringer Ingelheim International GmbH or one or more of its affiliated companies. All rights reserved.

This document may not - in full or in part - be passed on, reproduced, published or otherwise used without prior written permission.

dose on, the “missed” dose should be omitted. A double dose to make up for missed individual doses must not be taken.

Any patient that decides to discontinue study medication should be considered for a switch to an appropriate (non-study) anticoagulant according to local practice. For patients receiving dabigatran etexilate, continuation of study drug for 2-3 days to assist bridging may be appropriate. For recommendations on how to switch from dabigatran etexilate to other anticoagulants see [Appendix 10.2](#)).

Patient randomised to receive warfarin:

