Re-administration of study medication (at the same dose as before) after the bleeding has resolved and haemostasis has been achieved, is at the discretion of the Investigator. In the case of a temporary stop of dabigatran etexilate bridging therapy with a parenteral anticoagulant with e.g. UFH or LMWH (according to local practice) is at the discretion of the Investigator. See [Appendix 10.1](#) for additional information related to bridging.

A summary of how to manage bleedings on dabigatran etexilate is presented in [Figure 4.2.1.1: 1](#).

Proprietary confidential information.

© 2016 Boehringer Ingelheim International GmbH or one or more of its affiliated companies. All rights reserved.

This document may not - in full or in part - be passed on, reproduced, published or otherwise used without prior written permission.

[figure not shown]

Figure 4.2.1.1: 1 Management of bleeding on dabigatran therapy [[P10-03790](#)]

Warfarin Treated Group:

If a patient experiences a major bleed warfarin should be temporarily stopped. The anticoagulant effect of VKAs can be reversed with vitamin K, prothrombin complex concentrates and/or fresh frozen plasma. Re-administration of warfarin after the bleeding has resolved and haemostasis has been achieved is at the discretion of the Investigator. Bridging therapy, e.g. UFH until the INR has returned back to the target range, is at the discretion of the Investigator (see [Appendix 10.1](#)).

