5.2 SAFETY

5.2.1 Endpoints of safety

The primary endpoint for this trial is time to first ISTH MBE or CRNMBE. For definition of CRNMBE see [section 5.2.2.1](#).

Proprietary confidential information.

© 2016 Boehringer Ingelheim International GmbH or one or more of its affiliated companies. All rights reserved.

This document may not - in full or in part - be passed on, reproduced, published or otherwise used without prior written permission.

Other safety endpoints are:

1. Major bleeding (ISTH)
2. CRNMBE (for definition see [section 5.2.2.1](#))
3. Clinically relevant bleeding measured using the following definitions:
 - Bleeding Academic Research Consortium (BARC) ≥ 3
 - TIMI group - Major and Minor
4. Minor and total bleeding (ISTH, BARC and TIMI)
5. Intracranial haemorrhage

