5.2.2 Assessment of adverse events

5.2.2.1 Assessment of Bleeding events

Patients should be carefully assessed for signs and symptoms of bleeding. Bleeding will be classified as major, Clinically Relevant Non Major Bleeding Event (CRNMBE) or minor. Major bleeds will be further sub classified as life-threatening and other major bleeds. The location of the bleeding including the specific critical area or organ into which the bleeding occurred and whether or not it prolongs hospitalisation will be recorded. The following definitions are specified for bleeds:

Definition of a major bleed

Major bleeds will be defined according to the ISTH definition of a major bleed, as follows [[R05-0344](#)].

- Symptomatic bleeding in a critical area or organ, such as intracranial, intraspinal, intraocular, retroperitoneal, intra-articular or pericardial, or intramuscular with compartment syndrome

and/or

- Bleeding associated with a reduction in haemoglobin of at least 2g/dL (1.24mmol/L), or leading to transfusion of two or more units of blood or packed cells¹

and/or

- Fatal bleed

Definition of a CRNMBE

A clinically relevant non-major bleeding event is a clinically overt bleed that does not meet

¹ Bleeding should be overt and the haemoglobin drop should be considered to be due to and temporally related to the bleeding event.

the criteria for a major bleed but prompts a clinical response, in that it leads to at least one of the following:

- A hospital admission for bleeding
- or
- A physician guided medical or surgical treatment for bleeding
- or
- A physician guided change, interruption¹ or discontinuation of study drug.

Definition of a minor bleed

Minor bleeds are clinical bleeds that do not fulfil the criteria for major bleeds. Minor bleeds will be further divided to those that are CRNMBE, (see above) and those that are not.

Definition of a life-threatening bleed

Major bleeds are to be classified as life-threatening if they meet one or more of the following criteria:

- Fatal, or symptomatic intracranial bleed; reduction in haemoglobin of at least 5g/dL; transfusion of at least four units of blood or packed cells, associated with hypotension requiring the use of i.v. inotropic agents; necessitated surgical intervention.

Definition of intracranial haemorrhage (ICH)

Intracranial haemorrhage (ICH) comprises the subtypes of intracerebral bleeds, subdural bleeds, epidural bleeds and subarachnoid bleeds and will be recorded.

Definition of a fatal bleeding

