Fatal bleeding is defined as a bleeding event that the IAC determines is the primary cause of death or contributes directly to death.

Total bleeds

This is the sum of all major and minor bleeds.

In addition to the specified primary definition to be used for major bleeds in this trial (according to ISTH criteria, see above), components of the further bleeding definitions will be prospectively collected. It will be the responsibility of the IAC to categorise investigator-reported bleeding events according to the following pre-specified secondary classifications:

- **BARC** ([R13-4065](#), [R13-4066](#))
- **TIMI** ([P07-10190](#))

TIMI Classification of Bleeding

¹ Interruption of study drug (more than omitting one dose) due to the bleeding event.

The TIMI definition of bleeding uses four categories: major, minor, minimal and none, with definitions of the first three as follows:

- Major
Intracranial haemorrhage or a ≥ 5 g/dL decrease in haemoglobin concentration or a $\geq 15\%$ absolute decrease in haematocrit
- Minor
Observed blood loss: ≥ 3 g/dL decrease in haemoglobin concentration or $\geq 10\%$ decrease in haematocrit.
No observed blood loss: ≥ 4 g/dL decrease in haemoglobin concentration or a $\geq 12\%$ decrease in haematocrit
- Minimal
Any clinically overt sign of haemorrhage (including imaging) associated with a < 3 g/dL decrease in haemoglobin concentration or $< 9\%$ decrease in haematocrit.

BARC Definition for Bleeding¹

Type 0: no bleeding

Type 1: bleeding that is not actionable and does not cause the patient to seek unscheduled performance of studies, hospitalisation, or treatment by a healthcare professional; may include episodes leading to self-discontinuation of medical therapy by the patient without consulting a healthcare professional

Type 2: any overt, actionable sign of haemorrhage (e.g., more bleeding than would be expected for a clinical circumstance, including bleeding found by imaging alone) that does not fit the criteria for type 3, 4, or 5 but does meet at least one of the following criteria: (1) requiring nonsurgical, medical intervention by a healthcare professional, (2) leading to hospitalisation or increased level of care, or (3) prompting evaluation

Type 3:

- Type 3a
 - Overt bleeding plus haemoglobin drop of 3 to < 5 g/dL* (provided haemoglobin drop is related to bleed)
 - Any transfusion with overt bleeding

¹ Footnotes to BARC definition:

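### The CRNMBE interruption threshold is counted in omitted doses, so it is about one day on twice-daily dabigatran and about two days on once-daily warfarin

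*Protocol*

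**What the plan says.** Protocol 5.2.1 sets the endpoint: "The primary endpoint for this trial is time to first ISTH MBE or CRNMBE". Under 5.2.2.1 a clinically overt bleed that is not major is a CRNMBE if it leads to any one of three responses: admission for the bleed, physician-guided treatment of it, or (criterion 3) "A physician guided change, interruption" "or discontinuation of study drug". A footnote attached to the interruption limb reads "Interruption of study drug (more than omitting one dose) due to the bleeding event". The *change* limb has no footnote and no definition.

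The regimens are in 4.1.1. For dabigatran 110 mg it is "1 x 110mg capsule b.i.d. (total daily dose 220mg", and the 150 mg arm is also twice daily. Section 4.1.4 adds "The interval between doses should be as close to 12 hours as possible". For the comparator, "Patients will take the warfarin q.d", with the dose titrated to INR.

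For minor bleeds, 4.2.1.2 leaves continuing, interrupting or stopping study drug to the investigator, who is not blinded (4.1.5.1). The end of 5.2.2.1 has the adjudication committee apply the protocol's definitions, as outlined in its charter. SAP 5.1 refers back to the protocol for the ISTH criteria and to the charter for adjudication criteria. Neither document converts the dose count into a common unit of time.

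**The concern.** A rule counted in doses is not the same rule on two dosing frequencies. Take an overt nuisance bleed for which the physician withholds the anticoagulant for one day and does nothing else. On dabigatran it is a primary-endpoint event; on warfarin, under the interruption limb, it is not. Blinded adjudication cannot remove this, because the committee would be applying correctly a rule that is itself unequal.

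The *change* limb may be unequal the other way. Warfarin is adjusted throughout the trial, while dabigatran has a fixed assigned dose. If a dose reduction prompted by a bleed counts as a change, warfarin patients have more occasion to meet it.

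The endpoint carries four of the six confirmatory steps in Protocol 7.2: non-inferiority of each dose (Steps 1 and 2) and superiority of each dose (Steps 4 and 6). Extra dabigatran-only events make non-inferiority harder to show. Extra warfarin-only events make both non-inferiority and superiority easier to claim.

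**Working it through.** **The plan's own figures.** Inputs from Protocol 7.2 and 7.6: one-sided alpha 0.025, margin 1.38, 167 events per arm (334 per pair), 834 patients per arm, 14% with an event at one year, stated power 83.6%. The true hazard ratio used for power is not stated; I take it as 1.

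- Power = Φ(ln 1.38 / √(1/167 + 1/167) − 1.96) = Φ(0.3221/0.1094 − 1.96) = Φ(0.983) = 83.7%, against 83.6%.
- Events: yearly rate λ = −ln 0.86 = 0.1508, with follow-up uniform from 0.5 to 2.5 years. P(event) = 1 − (e^(−0.5λ) − e^(−2.5λ))/(2λ) = 0.1994, and 834 × 0.1994 = 166.3, against 167.

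The sample-size figures reproduce and are not in dispute.

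**The dose count.** Doses omitted = hours withheld / dosing interval; the footnote needs more than 1.

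- Dabigatran, 24-hour hold: 24/12 = 2 doses, which qualifies. Protocol Table 4.2.1.3: 1 likewise equates a 24-hour stop with two doses.
- Warfarin, 24-hour hold: 24/24 = 1 dose, which does not qualify.
- Shortest qualifying hold (2 doses): 2 × 12 = 24 h on dabigatran, 2 × 24 = 48 h on warfarin.

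**Who is affected.** Admission or physician-guided treatment makes the bleed a CRNMBE in any arm, whatever the length of the hold. The gap therefore concerns only overt, non-major bleeds whose sole response was a physician-guided hold long enough to qualify on dabigatran but not on warfarin.

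**Illustration of size.** The documents do not give the share of patients affected, so the shares p below are assumptions. Each route is taken alone, with 167 events kept in the unaffected arm.

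- Let r = (167 + 834p)/167 and SE = √(1/167 + 1/(167 + 834p)).
- Hold route (extra events in one dabigatran arm, true HR 1): observed HR = r; power = Φ((ln 1.38 − ln r)/SE − 1.96).
- Change route (extra events in warfarin, true HR 1.38): observed HR = 1.38/r; one-sided error = Φ(ln r/SE − 1.96).

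For p = 1%: 834p = 8.34, r = 175.34/167 = 1.050, SE = 0.1081. Power = Φ((0.3221 − 0.0487)/0.1081 − 1.96) = Φ(0.57) = 71.5%. Error = Φ(0.0487/0.1081 − 1.96) = Φ(−1.51) = 6.6%.

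| Assumed p | Extra patients | Hold route: HR, power | Change route: HR, error |
|---|---|---|---|
| 0.5% | 4.2 | 1.02, 78.1% | 1.35, 4.2% |
| 1% | 8.3 | 1.05, 71.5% | 1.31, 6.6% |
| 2% | 16.7 | 1.10, 56.4% | 1.25, 14.2% |

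With equal shares on both routes and a true HR of 1, the observed HR is (167 + 834p)/(167 + 834p) = 1: the effects cancel.

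**Whether a planned analysis would show it.** The sensitivity analyses of the primary composite in SAP 7.4 are on-treatment (treated and per-protocol sets), non-elderly patients, investigator-reported events, and non-assessable events counted as positive. None removes events that qualify only through criterion 3.

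**The case against.** The strongest reply accepts the dose arithmetic and disputes what follows from it.

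- **Charter.** Protocol 3.1.1 says the adjudication charter holds detailed endpoint definitions. It is not among the documents and might harmonise the rule. That cannot be excluded, but 5.2.2.1 and SAP 5.1 both point to the protocol's definitions, so the protocol text should itself be regimen-neutral.
- **Change.** A reader might infer that a change can happen only in the warfarin arm. The documents do not say so. The criterion refers to a change of study drug, not of dose. The phrase "Re-administration of study medication (at the same dose as before" stands under major bleeds, whereas a CRNMBE is non-major; 4.2 only asks that resuming the assigned dose be considered. Warfarin titration is tied to INR, not to bleeding. A committee might also class one physician-omitted warfarin dose as a change, which would narrow the hold gap.
- **Blinding.** A reader might infer that a dose-count rule reveals the arm. This is not shown: a yes/no field for more than one omitted dose needs no dosing frequency, and 2.3 and 3.1.1 provide for blinded packets.
- **Size.** The shares are assumed, and 2% already means about 10% of an arm's events (16.7/167). The error figures are errors relative to an endpoint with an equal rule, not to the endpoint as the protocol defines it. Both limits stand.
- **Other endpoints.** SAP 7.8.5 analyses ISTH major bleeding, BARC ≥3, TIMI and total bleeding by the primary method, and these do not turn on the dose threshold. They give useful context, but none is the primary composite without the affected events.
- **Equal time is not equal anticoagulation.** Dabigatran's effect wears off faster (2.3, Appendix 10.1.3). True, but a count of doses does not correct for that either.

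**Conclusion.** The interruption threshold differs by arm on the plain text, about one day against about two, and no planned sensitivity analysis of the primary composite would expose it. That rests on the two dosing intervals and the footnote alone. It reaches only bleeds whose sole response was a physician-guided hold. The opposing effect through *change* is plausible but rests on an undefined word.

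A reader might go further and call the trial biased for or against dabigatran. The documents do not support that: the hold route acts against non-inferiority, the *change* route acts towards it, neither share is given, and equal shares cancel. Cancellation would, however, be coincidence. The power and error figures show only that a handful of patients per arm, about 8 at 1%, would be enough to matter. The point is worth correcting because the remedy is cheap and the endpoint carries four confirmatory steps; it does not by itself undermine the design.

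**What to change.** These changes concern event classification only and leave the management of bleeds untouched.

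1. In the 5.2.2.1 footnote, state the threshold in whole days of scheduled study anticoagulant withheld because of the bleed, with the same number of days in all arms. Say whether a dose adjustment prompted by a bleed counts as a *change*. Whole days matter: a threshold of more than 24 hours withheld would still need three dabigatran doses (36 h) against two warfarin doses (48 h). Time since last intake would reverse the gap, because one omitted dose leaves 48 h between intakes on warfarin and 24 h on dabigatran.
2. Have the committee record which CRNMBE criterion or criteria each event met.
3. In SAP 7.4, add a sensitivity analysis of the primary endpoint that excludes CRNMBEs qualifying only through criterion 3.

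The cost is one footnote, one adjudication-form field and one further Cox model per comparison. Already adjudicated criterion-3-only events need a recheck, and the sensitivity analysis will have slightly fewer events. Changing the footnote also means rechecking the 14% event proportion, which came from blinded data of this trial. If the footnote is left as it is at this stage, items 2 and 3 should still be done.

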5.2.2.2 Definitions of AEs

AE

¹ Footnotes to BARC definition:

CABG indicates coronary artery bypass graft. Platelet transfusions should be recorded and reported but are not included in these definitions until further information is obtained about the relationship to outcomes. If a CABG-related bleed is not adjudicated as at least a type 3 severity event, it will be classified as not a bleeding event. If a bleeding event occurs with a clear temporal relationship to CABG (i.e., within a 48-hour time frame) but does not meet type 4 severity criteria, it will be classified as not a bleeding event.

*Corrected for transfusion (1 U packed red blood cells or 1 U whole blood = 1 g/dL haemoglobin).

†Cell saver products are not counted.

An AE is defined as any untoward medical occurrence, including an exacerbation of a pre-existing condition, in a patient in a clinical investigation who received a pharmaceutical product. The event does not necessarily have to have a causal relationship with this treatment.

SAE

An SAE is defined as any AE which results in death, is immediately life-threatening, results in persistent or significant disability / incapacity, requires or prolongs patient hospitalisation, is a congenital anomaly / birth defect, or is to be deemed serious for any other reason if it is an important medical event when based upon appropriate medical judgement which may jeopardise the patient and may require medical or surgical intervention to prevent one of the other outcomes listed in the above definitions.

Intensity of AE

The intensity of the AE should be judged based on the following:

Mild: Awareness of sign(s) or symptom(s) which is/are easily tolerated
Moderate: Enough discomfort to cause interference with usual activity
Severe: Incapacitating or causing inability to work or to perform usual activities

Causal relationship of adverse event

Medical judgment should be used to determine the relationship, considering all relevant factors, including pattern of reaction, temporal relationship, de-challenge or re-challenge, confounding factors such as concomitant medication, concomitant diseases and relevant history. Assessment of causal relationship should be recorded in the case report forms.

For Japan: The reason for the decision on causal relationship needs to be provided in the eCRF.

Yes: There is a reasonable causal relationship between the investigational product administered and the AE.
No: There is no reasonable causal relationship between the investigational product administered and the AE.

Outcome Events

Since efficacy and safety endpoints can also be SAEs, they can be treated as disease-related. These events will not be reported as SAEs on the SAE form and consequently will not be reported in an expedited manner to the Competent Authorities. For handling of OEs, please see [Appendix 10.4](#).

A key remit of the independent DMC is to protect patient safety by monitoring the incidence and clinical relevance of safety data collected throughout the conduct of this study.

In addition, for the safety parameters of primary interest, namely any bleeding event (see [Section 5.2.2.1](#)) and for the major mortality/morbidity clinical endpoints of interest (see

Proprietary confidential information.

© 2016 Boehringer Ingelheim International GmbH or one or more of its affiliated companies. All rights reserved.

This document may not - in full or in part - be passed on, reproduced, published or otherwise used without prior written permission.

[Section 5.2.2.2](#) and [Section 5.1.2](#)), a blinded IAC will be in place with the responsibility to confirm and classify all such events.

Any OE that occurs prior to randomisation and fulfils the criteria of an SAE will be reported in the standard expedited fashion as an SAE; however, if the patient has been randomised, these events will not be reported as SAEs, but entered in the eCRF as OEs.

OEs are therefore defined as follows:

- Any bleed
- All deaths
- All MIs
- All strokes
- All SE
- All TIAs
- All stent thromboses

The Investigator (or designee) will enter these OEs (even if they meet the criteria of an SAE) in the corresponding pages in the eCRF within 24 hours of awareness, as well as providing any defined supporting documentation (including imaging e.g. MR, CT, angiography). This will be provided by the Sponsor to the DMC and IAC, as defined in their respective charter. This procedure is defined in more detail in [Appendix 10.4](#).

Worsening of the underlying disease or other pre-existing conditions

Worsening of the underlying disease or of other pre-existing conditions will be recorded as an (S)AE in the eCRF.

Changes in vital signs, ECG, physical examination and laboratory test results

Changes in vital signs, ECG, physical examination and laboratory test results will be recorded as an (S)AE in the eCRF if they are judged clinically relevant by the Investigator.

Protocol-specified Adverse Events of Special Interest (AESI)

No AESIs are defined for this trial.

Residual effect period (REP)

The residual effect period (REP) is the time period after the last dose administration of trial medication when measurable drug levels or PD effects are still likely to be present. Events

Proprietary confidential information.

© 2016 Boehringer Ingelheim International GmbH or one or more of its affiliated companies. All rights reserved.

This document may not - in full or in part - be passed on, reproduced, published or otherwise used without prior written permission.

occurring in the REP are handled as occurring on treatment. The residual effect period is defined as 6 days after last intake of trial medication.

